 - Number of subjects experiencing an SAE or Grade 3 AE, in the same SOC grouping of Preferred Terms based on Medical Dictionary for Regulatory Activities (MedDRA) coding, considered to be related to RD-X19.

Safety and tolerability (local reactogenicity) will be assessed actively on each clinic visit by review of potential adverse events (AEs) and targeted physical examination, as required. Volunteers will be encouraged to contact designated clinical trial staff for AEs of a medically-urgent nature as soon as is practically possible and to seek immediate medical care, if needed.

Metabolic, liver, kidney and hematological laboratory evaluations will be performed at screening and at Day 8 or early termination (and potentially during unscheduled) clinic visits.

Study Subject safety will be monitored throughout the study by the Investigator and supported by regular review by the Medical Monitor and an external Data Monitoring Committee.

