3.2 Sample Size Determination

The study is hypothesis generating in nature. Hence, the sample size was selected for convenience.

The target number of subjects randomized is 60 in total, and 30 per cohort (20 subjects to RD-X19 and 10 subjects to sham).

4 Populations To Be Analyzed

Three subject populations are defined as follows:

- (1) Safety: This population will include all subjects who receive at least 1 study treatment. The Safety Population will be used for analysis of safety and tolerability data. Subjects will be analyzed based on actual treatment received.
- (2) Intent-to-Treat (ITT): This population will include all randomized subjects who receive treatment and were not discontinued due to a significant abnormality from the baseline CMP and CBC tests. This population will be used for all efficacy analyses as the primary population. Subjects will be analyzed based on randomized treatment, regardless of the actual treatment received.
- (3) Per-Protocol Population (PP): This population will include subjects who complete the study and did not have a major protocol deviation (MPD). The PP population will be used for supportive analysis of the efficacy endpoints. MPDs are those that could have interfered with the administration of treatment or the precise evaluation of treatment efficacy.

MPDs may include but will not be limited to the following:

- Violation of inclusion/exclusion criteria;
- Use of prohibited concomitant medications during the treatment period;
- No Day 3 Visit;

- Returned for Day 8 Visit outside the designated visit window;
- Was not compliant with the dosing regimen.

All MPDs will be identified before the database lock and study unblinding for analysis.

5 Planned Analyses

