5.5.1 Analysis of Primary Efficacy Endpoint

The primary efficacy endpoint is defined as time-weighted average (TWA) change in log10-transformed viral load by RT-qPCR from baseline to Day 8, where TWA will be derived using the trapezoidal rule:

$$\frac{\sum_{i=a}^{b-1} \{0.5 \times (Y_i + Y_{i+1}) \times (t_{i+1} - t_i)\}}{(t_b - t_a)}$$

Y_i is the change from baseline in log10-transformed viral load by RT-qPCR at Visit i , t is the actual study day at the specified timepoint, a is the baseline visit at Day 1, and b is the Day 8 visit.

At the final analysis, each dose of the RD-X19 device will be compared to sham using an Analysis of Covariance (ANCOVA) model with baseline viral load on log10 scale as a covariate and treatment group as an independent variable.

An example of SAS code for the analysis is as follows:

```
proc glm data=datain;
  class trt;
  model aval = trt base /ss3;
  estimate '4x RD-X19 vs Sham' trt 1 0 -1;
  estimate '7x RD-X19 vs Sham' trt 0 1 -1;
  lsmeans trt /pdiff stderr cl;
run;
```

where AVAL denotes the variable to be analyzed, BASE denotes the covariate baseline value, and TRT denotes treatment group with values 1 for 4 Days RD-X19, 2 for 7 Days RD-X19, and 3 for Sham.

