5.6.4 Other Assessments

Following assessment results will be presented in subject data listing: medical history, physical examination, clinical laboratory evaluations, concomitant medications.

Interim Analysis

Upon completion of all subjects in Cohort 1, an unblinded interim analysis will be conducted focusing on the following evaluations:

- Efficacy:
 - Geometric mean viral load as measured in saliva on day 1, 3, 5 and 8 by RT-qPCR
 - Proportion of subjects demonstrating viral load reduction $\geq 95\%$ on day 3, 5 and 8 by RT-qPCR.
 - Time to alleviation of COVID-19 signs and symptoms
 - Time to sustained alleviation of COVID-19 signs and symptoms
- Safety:
 - All safety tabulations as listed in section 5.6.1 will be assessed as part of the interim analysis.
 - Summary of Treatment Emergent Adverse Events including a review of listings to monitor:
 - Number of study subjects experiencing any Serious Adverse Reaction (SAE).
 - Number of study subject experiencing treatment site reactions, including pain, induration or erythema of the oropharynx or oral mucosa, including the uvula and tongue.
 - Number of study subjects with any laboratory result that is out-of-range using the testing laboratory's institutional standards, including blood, urine and methemoglobin measured by pulse oxymetry.
 - Number of subjects experiencing laryngospasm, bronchospasm or anaphylaxis within 2 hours after use of the RD-X19 Device that is considered related to RD-X19.
 - Number of subjects experiencing an allergic reaction such as generalized urticaria (defined as occurring at three or more body parts) within 72 hours after use of study treatment that is considered related to RD-X19.
 - Number of subjects experiencing Grade 3 TEAE, in the same SOC grouping of PT, considered to be related to RD-X19.

As study subjects in cohort 1 are essentially a separate study, there is no prohibition to sponsor being unblinded for the interim analysis. Cohort 1 subjects are not tied to cohort 2 in any way and unblinding data from cohort 1 has no operational or statistical implications for cohort 2 assessment by sponsor. Study site personnel may not be unblinded to cohort 1 as there is a reasonable possibility that this information could be the basis for bias in the assessment of cohort 2.

To meet above review interest, the following summary tables (treatment groups: 4 Days RD-X19 vs. Sham) and by-subject data listings will be prepared for the interim analysis:

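### The SAP allows sponsor unblinding at the Cohort 1 interim because the cohorts are said to be unconnected, but its final model puts Cohort 1 sham into the Cohort 2 contrast

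*Combined protocol and SAP*

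**What the plan says.** The Interim Analysis text that follows SAP section 5.6.4 treats Cohort 1 as in effect its own study and concludes that "there is no prohibition to sponsor being unblinded for the interim analysis". The reason given is that "Cohort 1 subjects are not tied to cohort 2 in any way and unblinding data from cohort 1 has no operational or statistical implications", a claim the sentence then limits to the sponsor's assessment of Cohort 2. The same paragraph keeps site personnel blinded to Cohort 1 because that knowledge might bias how Cohort 2 is assessed.

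SAP section 5.5.1 sets the final primary analysis. The model is "model aval = trt base /ss3", where "TRT denotes treatment group with values 1 for 4 Days RD-X19, 2 for 7 Days RD-X19, and 3 for Sham". The Cohort 2 comparison is "estimate '7x RD-X19 vs Sham' trt 0 1 -1".

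On deviations, SAP section 4 says "All MPDs will be identified before the database lock and study unblinding for analysis". It gives no separate date for Cohort 1.

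On oversight, the amended protocol strikes the word independent from the description of the safety monitoring team (sections 4.1.2 and 6.1), while section 6.1 still promises "regular review by the Medical Monitor and an external Data Monitoring Committee".

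**The concern.** The permission to unblind rests on a factual claim about how the two cohorts relate. If Cohort 1 sham subjects are also controls for the 7-day arm, the claim is false. Part of the final Cohort 2 comparison is then known by arm, to whoever at the sponsor is unblinded, before Cohort 2 is complete.

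What is at stake is discretion used after the interim. Per-protocol membership of Cohort 1 subjects feeds the per-protocol version of the 7-day contrast (Table 14.2.1.2). Changes to the analysis can affect the intention-to-treat version too. The SAP does not require either to be settled before Cohort 1 results are seen. A reader of the final report could also use the SAP's own wording to challenge the 7-day result.

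**Working it through.** **Inputs.** SAP section 3.2: 60 randomized, 30 per cohort, 20 RD-X19 and 10 sham in each. Check: 2 × (20 + 10) = 60, which agrees. SAP section 5.5.1: treatment factor with three levels, baseline covariate, no cohort term. The documents give no SD, so results are in units of the residual SD, s. The hand calculation ignores the baseline covariate.

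**1. Are the cohorts tied in the model?** Only one Sham level exists, so sham subjects from both cohorts share it. The final shells (for example Tables 14.1.1, 14.2.1.1, 14.2.3 and 14.2.5.1) also have one Sham column. Cohort 1 subjects further contribute to the common baseline slope and residual variance. No current section defines a Cohort 2-only control.

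**2. Share of the 7-day contrast.** Write A4 and A7 for the active means and S1 and S2 for the sham means by cohort.
- Final contrast: A7 − (S1 + S2)/2.
- Variance: s²[1/20 + (1/4)(1/10) + (1/4)(1/10)] = s²(0.050 + 0.025 + 0.025) = 0.100 s², so SE = 0.316 s.
- Cohort 1 sham: 10 of 20 controls (50%), and 0.025/0.100 = 25% of the variance.

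**3. Correlation with what is unblinded.** The interim set includes the primary endpoint by arm for Cohort 1 (Table 14.2.1.1).
- Interim contrast: A4 − S1. Variance: s²(1/20 + 1/10) = 0.150 s², so SE = 0.387 s.
- Covariance with the final 7-day contrast, through S1: (1/2)(1/10)s² = 0.05 s².
- Correlation: 0.05/(0.387 × 0.316) = 0.41.
- A 20,000-run simulation of the three-level ANCOVA (assumed baseline slope 0.3) gave 0.41. Comparing the 7-day arm with Cohort 2 sham only gave 0.00, as truly separate cohorts should.

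**4. With the permitted overage.** Clarification Memorandum #2 allows 36 per cohort, which is 24:12 if 2:1 is kept. Cohort 1 then supplies 12 of 24 controls. The 50%, 25% and 0.41 are unchanged.

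**5. Operational link.** SAP section 3.1 has the Cohort 1 results reviewed, a recommendation made to the sponsor, and the next schedule chosen from it. The Cohort 1 review therefore has operational consequences for Cohort 2.

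**6. Timing of deviation decisions.** The interim tables use only the ITT and Safety populations, so nothing in the interim forces per-protocol membership to be settled first. The list of major deviations in SAP section 4 is open-ended, and SAP section 6 lets outputs be modified during analysis.

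**7. Cost of a within-cohort comparison.** 7-day versus Cohort 2 sham (20 v 10): SE = sqrt(1/20 + 1/10) = 0.387 s, against 0.316 s pooled. The ratio is 1.22.

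**The case against.** The best defence has several parts, and much of it stands.

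- The claim is confined to the sponsor's assessment of Cohort 2. That is a fair reading, but the final 7-day contrast is part of that assessment, so the claim still fails.
- Pooling is never stated in words. The SAS code is labelled an example and the shells may change. This stands as a limit, but the SAP offers no alternative.
- Pooling sham is a legitimate choice for precision, and the 25% and 0.41 would be the same under full blinding. They show that the cohorts are tied. They do not estimate bias.
- Exposure is narrow. The interim by-subject listings cover adverse events, out-of-range laboratory results, reactogenicity, oropharyngeal findings and methemoglobin, with no viral-load or diary data. Their shells are grouped by treatment, however, so allocation is visible. The CRO handles the data and analysis (protocol 11.1.5). ITT membership does not depend on major deviations, and the per-protocol analysis is only supportive.

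A reader might infer more than the documents support:

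- **That no firewall exists.** Site personnel stay blinded to Cohort 1, and a committee charter is cited that is not among the documents. Unblinding Cohort 1 does not reveal Cohort 2 allocation.
- **That the deviation rule is impossible to meet.** It can be met if Cohort 1 review is finished before the interim; the SAP just does not require that.
- **That the sponsor's TCID50 analysis is compromised by the interim.** SAP section 5.5.3 places it after study unblinding anyway.
- **That sample handling could be affected.** Blinded sites collect the specimens and a central laboratory runs the RT-qPCR (protocol 9.3).
- **That the sponsor-requested SAP amendment followed unblinding.** Nothing in the documents shows this.

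**Conclusion.** The stated ground for sponsor unblinding is wrong under the SAP's own final analysis. Half of the controls in the 7-day contrast, carrying 25% of its variance, come from the cohort unblinded early, and the contrast correlates about 0.41 with the interim result. The claim of no operational implications also fails, because the Cohort 1 review sets the Cohort 2 schedule.

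The practical exposure is limited to supportive per-protocol membership and any analysis changes made after the interim. No bias has been quantified. The figures assume the planned 20:10 allocation, equal residual variance, independent subjects, and that the pooled three-level model is the one used; s cancels from the shares and the correlation.

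Severity is modest. SAP sections 3.2 and 5.1 describe a hypothesis-generating trial with a convenience sample and descriptive, unadjusted p-values. The correction should still be made, since it costs little.

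**What to change.** 1. Delete the statements that the cohorts are unconnected and that unblinding has no implications. State instead that Cohort 1 sham subjects enter the final contrasts.
2. Before interim unblinding, lock Cohort 1 data, Cohort 1 major deviations and per-protocol membership, and the final efficacy analysis. Label any later change as made after unblinding.
3. Name the sponsor roles that are unblinded. Limit subject-level allocation to the safety monitoring team and an unblinded statistician.
4. Reconcile the oversight wording in protocol sections 4.1.2 and 6.1, so that it is clear whether the reviewing body is independent and whether an external committee exists.
5. Keep the pooled contrast if its precision is wanted, and add 7-day versus Cohort 2 sham as a sensitivity analysis. This is needed because group summaries alone still disclose the Cohort 1 sham mean. Its standard error is 0.387 s against 0.316 s, about 22% larger.

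The cost is SAP wording, one extra comparison, an earlier deviation review for Cohort 1, and less subject-level detail for sponsor staff until final lock. Sample size, safety review and clinical conduct do not change.

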7.1 Study Schedule of Activities

The schedule of visits and procedures to be conducted at each visit are summarized in the Study Schedule of Activities.

Study Procedures	Screening, Enrollment & Randomization	Follow-up Period (Visit Window)			
		1	2	3	5 (-1 to +1)
Study Days		1	2	3	5 (-1 to +1)
Informed Consent		X			
COVID19 Screening & SARS-CoV-2 Rapid Antigen Test***		X			
Medical History & Physical Examination		X	Changes since last visit only	Changes since last visit only	Changes since last visit only
Oropharyngeal Assessment		X*	Changes since last visit only	Changes since last visit only	Changes since last visit only
Urine Pregnancy Test		X			X
Concomitant Medication History/New		Baseline	Changes since last visit only	Changes since last visit only	Changes since last visit only
Comprehensive Metabolic Panel & CBC		X			X
Vital Signs		X			X
Methemoglobin		X			X
Adverse Event Assessment / Reactogenicity		Baseline	X	X	X
Demographics, Inclusion / Exclusion Review		X			
Diary Dispensation/Collection		X			X
Treatment at Site		X**	X**	X**	
Biospecimen collection for viral assays (3 specimens)****		X		X	X
COVID-19 Severity Score		X			X
Collect RD-X19 Device		NA			Cohort 1
					Cohort 2

*On Day 1 to be evaluated 30 minutes after first illumination at site.

**Only one treatment will be done on site, other treatment will be done at home, i.e. if afternoon appointment, subject will complete morning treatment at home and afternoon treatment administered at the site. For scheduling purposes, recommended interval between treatment is approximately 8 – 12 hours but not \leq 4 hours.

***Subjects presenting at the time of screening that have tested positive via a SARS-CoV-2 rapid antigen test at or within the past 24 hours of the screening visit and can provide documentation confirming proper identification, the date of the test and testing location, positivity of the result, and name/identity of the assay used to generate the result, are also eligible for enrollment and the rapid antigen test does not have to be repeated at the site.

**** At Baseline and days 3, 5, and 8, subjects will provide two saliva specimens and an oropharyngeal swab for virology endpoint assessments. One saliva specimen will be collected, preserved, and shipped fresh to a central lab for assessment of SARS-CoV-2 mRNA via RT-qPCR. The second specimen and the oropharyngeal swab will be collected in separate collection tubes, frozen, and stored at the site and shipped to a central lab at the end of each cohort.

7.2 List of Summary Tables, Data Listings and Figures

List of Summary Tables

Number	Description	Analysis Set	Source Listing(s)
14.1	Demographic and Baseline Data Summaries		
14.1.1	Subject Final Study Disposition	All Randomized Subjects	16.2.1
14.1.2	Subject Analysis Population	All Randomized Subjects	16.2.1, 16.2.2.1
14.1.3	Demographic and Baseline Characteristics	Safety Population	16.2.4.1, 16.2.9.3
14.2	Efficacy Data Summary Tables		
14.2.1.1	Time-Weighted Average Change in Log10-Transformed Viral Load by RT-qPCR from Baseline to Day 8	ITT Population	16.2.6.4
14.2.1.2	Time-Weighted Average Change in Log10-Transformed Viral Load by RT-qPCR from Baseline to Day 8	PP Population	16.2.6.4
14.2.2.1	Log10-Transformed Viral Load via RT-qPCR by Visit	ITT Population	16.2.6.4
14.2.2.2	Log10-Transformed Viral Load via RT-qPCR by Visit	PP Population	16.2.6.4
14.2.2.3	Proportion of Subjects with At Least 95% Reduction by Visit in SARS-CoV-2 Viral Load via RT-qPCR	ITT & PP Populations	16.2.6.3
14.2.3	Clearance of Viral Infection in Saliva via RT-qPCR	ITT & PP Populations	16.2.6.4
14.2.4	COVID-19 Composite Severity Score by Visit	ITT & PP Populations	16.2.6.1
14.2.5.1	Time to Alleviation of COVID-19 Symptoms	ITT & PP Populations	16.2.6.1.2, 16.2.5.3
14.2.5.2	Time to Sustained Alleviation of COVID-19 Symptoms	ITT & PP Populations	16.2.6.1.2, 16.2.5.3
14.3	Safety Data Summaries		
14.3.1.1	Treatment-Emergent Adverse Events by System Organ Class and Preferred Term	Safety Population	16.2.7
14.3.1.2	Treatment-Emergent Adverse Events by System Organ Class, Preferred Term and Severity	Safety Population	16.2.7
14.3.1.3	Treatment-Emergent Adverse Events by System Organ Class, Preferred Term and Causality to Study Device	Safety Population	16.2.7
14.3.1.4	Treatment-Emergent Adverse Events by System Organ Class, Preferred Term and Study Day of Most Severe Observation	Safety Population	16.2.7
14.3.2	Reactogenicity by Visit	Safety Population	16.2.9.1
14.3.3	Oropharyngeal Assessment by Visit	Safety Population	16.2.9.2
14.3.4	Vital Signs by Visit	Safety Population	16.2.9.3
14.3.5	Methemoglobin by Visit	Safety Population	16.2.9.6

List of Data Listings

Number	Description
16.2.1	Subject Disposition
16.2.2.1	Protocol Deviations
16.2.2.2	Informed Consent and Eligibility Criteria
16.2.2.3	General Comments
16.2.4.1	Demographics
16.2.4.2	Medical/Surgical History
16.2.5.1	Subject Randomization, Dosing Diary and Study Device Dispensing at Visit 1/Day 1, and Illumination Treatment at Site
16.2.5.2	Treatment Record and Subject Diary Collection at End of Study
16.2.5.3	Treatment Application Log
16.2.6.1.1	COVID-19 Symptom Assessment and Severity Score
16.2.6.1.2	COVID-19 Symptom Assessment and Severity Score from Subject Diary
16.2.6.2	Clearance of COVID-19 Symptoms
16.2.6.3	Viral Load via Saliva Specimen and Oropharyngeal Swab Collection
16.2.6.4	Derived Clearance of Viral Infection and Time-Weighted Average Change from Baseline in Log10-Transformed Viral Load via RT-qPCR
16.2.7	Adverse Events
16.2.8.1	Out-of-Range Results of Clinical Laboratory Tests
16.2.8.2	Pregnancy Test (Female Subjects Only)
16.2.9.1	Reactogenicity Assessment
16.2.9.2	Oropharyngeal Assessment
16.2.9.3	Vital Signs
16.2.9.4	Physical Examination
16.2.9.5	Prior and Concomitant Medications
16.2.9.6	Methemoglobin Measurement

List of Figures

Number	Description	Analysis Set
15.1.1	Kaplan-Meier Plot of Time to Clearance of Viral Infection	ITT Population
15.1.2	Kaplan-Meier Plot of Time to Clearance of Viral Infection	PP Population
15.2.1	Kaplan-Meier Plot of Time to Alleviation of COVID-19 Symptoms	ITT Population
15.2.2	Kaplan-Meier Plot of Time to Alleviation of COVID-19 Symptoms	PP Population
15.3.1	Kaplan-Meier Plot of Time to Sustained Alleviation of COVID-19 Symptoms	ITT Population
15.3.2	Kaplan-Meier Plot of Time to Sustained Alleviation of COVID-19 Symptoms	PP Population

Summary Tables

Table 14.1.1 – Subject Final Study Disposition

	Treatment Group			Total n (%)
	4 Days RD-X19 n (%)	7 Days RD-X19 n (%)	Sham n (%)	
Subjects Randomized	XX	XX	XX	XX
Subjects Completed Study	XX (XX.X)	XX (XX.X)	XX (XX.X)	XX (XX.X)
Subjects Discontinued	XX (XX.X)	XX (XX.X)	XX (XX.X)	XX (XX.X)
Reason for Discontinuations:				
Withdrawal by Subject	XX (XX.X)	XX (XX.X)	XX (XX.X)	XX (XX.X)
Adverse Event	XX (XX.X)	XX (XX.X)	XX (XX.X)	XX (XX.X)
Medication Code Unblinded	XX (XX.X)	XX (XX.X)	XX (XX.X)	XX (XX.X)
Lost to Follow-Up	XX (XX.X)	XX (XX.X)	XX (XX.X)	XX (XX.X)
Pregnancy	XX (XX.X)	XX (XX.X)	XX (XX.X)	XX (XX.X)
Physician Decision	XX (XX.X)	XX (XX.X)	XX (XX.X)	XX (XX.X)
Failure to Meet Entry Criteria	XX (XX.X)	XX (XX.X)	XX (XX.X)	XX (XX.X)
Other	XX (XX.X)	XX (XX.X)	XX (XX.X)	XX (XX.X)

Source: Listing 16.2.1

O:\Studies\EmitBio\EB-P12-01\Biometrics\Programs\Tables\xxx.sas ran on Month Day, Year at hh:mm on data from Month Day, Year.

Table 14.1.2 – Subject Population

	Treatment Group			Total n (%)
	4 Days RD-X19 n (%)	7 Days RD-X19 n (%)	Sham n (%)	
Randomized	XX	XX	XX	XX
Safety population	XX (XX.X)	XX (XX.X)	XX (XX.X)	XX (XX.X)
Exclusion from Safety population	XX (XX.X)	XX (XX.X)	XX (XX.X)	XX (XX.X)
Reason for exclusion from Safety:				
No record of first dose	XX (XX.X)	XX (XX.X)	XX (XX.X)	XX (XX.X)
Intent-to-Treat (ITT) population	XX (XX.X)	XX (XX.X)	XX (XX.X)	XX (XX.X)
Exclusion from ITT population	XX (XX.X)	XX (XX.X)	XX (XX.X)	XX (XX.X)
Reason for exclusion from ITT:				
No record of first dose	XX (XX.X)	XX (XX.X)	XX (XX.X)	XX (XX.X)
Discontinued due to a significant abnormality from the baseline CMP and CBC tests	XX (XX.X)	XX (XX.X)	XX (XX.X)	XX (XX.X)
Per-Protocol (PP) population	XX (XX.X)	XX (XX.X)	XX (XX.X)	XX (XX.X)
Exclusion from PP population	XX (XX.X)	XX (XX.X)	XX (XX.X)	XX (XX.X)
Reason for exclusion from PP				
No record of first dose	XX (XX.X)	XX (XX.X)	XX (XX.X)	XX (XX.X)
Discontinued due to a significant abnormality from the baseline CMP and CBC tests	XX (XX.X)	XX (XX.X)	XX (XX.X)	XX (XX.X)
Inclusion/exclusion criteria violation	XX (XX.X)	XX (XX.X)	XX (XX.X)	XX (XX.X)
...				

Subjects with multiple exclusion reasons are presented under each category of Reason for Exclusion as appropriate.

Source: Listing 16.2.1, 16.2.2.1

O:\Studies\EmitBio\EB-P12-01\Biometrics\Programs\Tables\xxx.sas ran on Month Day, Year at hh:mm on data from Month Day, Year.

Table 14.1.3 – Demographic and Baseline Characteristics for Safety Population

	Category	Treatment Group			Total
		4 Days RD-X19	7 Days RD-X19	Sham	
Age (Years)	N	XX	XX	XX	XX
	Mean ± SD	XX.X ± XX.X	XX.X ± XX.X	XX.X ± XX.X	XX.X ± XX.X
	Median	XX.X	XX.X	XX.X	XX.X
	Min, Max	XX, XX	XX, XX	XX, XX	XX, XX
Gender n (%)	Male	XX (XX.X)	XX (XX.X)	XX (XX.X)	XX (XX.X)
	Female	XX (XX.X)	XX (XX.X)	XX (XX.X)	XX (XX.X)
Ethnicity n (%)	Hispanic or Latino	XX (XX.X)	XX (XX.X)	XX (XX.X)	XX (XX.X)
	Not Hispanic or Latino	XX (XX.X)	XX (XX.X)	XX (XX.X)	XX (XX.X)
	Not Willing to Provide	XX (XX.X)	XX (XX.X)	XX (XX.X)	XX (XX.X)
Race n (%)	American-Indian or Alaska Native	XX (XX.X)	XX (XX.X)	XX (XX.X)	XX (XX.X)
	Asian	XX (XX.X)	XX (XX.X)	XX (XX.X)	XX (XX.X)
	Black or African-American	XX (XX.X)	XX (XX.X)	XX (XX.X)	XX (XX.X)
	Native Hawaiian or Other Pacific Islander	XX (XX.X)	XX (XX.X)	XX (XX.X)	XX (XX.X)
	White or Caucasian	XX (XX.X)	XX (XX.X)	XX (XX.X)	XX (XX.X)
Body Mass Index (kg/m ²)	Other	XX (XX.X)	XX (XX.X)	XX (XX.X)	XX (XX.X)
	N	XX	XX	XX	XX
	Mean ± SD	XX.X ± XX.X	XX.X ± XX.X	XX.X ± XX.X	XX.X ± XX.X
	Median	XX.X	XX.X	XX.X	XX.X
	Min, Max	XX, XX	XX, XX	XX, XX	XX, XX

Source: Listing 16.2.4.1, 16.2.9.3

O:\Studies\EmitBio\EB-P12-01\Biometrics\Programs\Tables\xxx.sas ran on Month Day, Year at hh:mm on data from Month Day, Year.

Table 14.2.1.1 – Time-Weighted Average Change in Log10-Transformed Viral Load by RT-qPCR from Baseline to Day 8 for Intent-to-Treat Population

	Statistics	4 Days RD-X19	7 Days RD-X19	Sham
TWA Change in Log10-Transformed Viral Load	N	XX	XX	XX
	Mean \pm SD	XX.X \pm XX.X	XX.X \pm XX.X	XX.X \pm XX.X
	Median	XX.X	XX.X	XX.X
	Min, Max	XX, XX	XX, XX	XX, XX
	LSM (SE)	XX (XX.X)	XX (XX.X)	XX (XX.X)
	95% CI for LSM	(XX.X, XX.X)	(XX.X, XX.X)	(XX.X, XX.X)
RD-X19 vs. Sham				
	LSMD (SE)	XX (XX.X)	XX (XX.X)	
	95% CI for LSMD	(XX.X, XX.X)	(XX.X, XX.X)	
	P-value	0.XXX	0.XXX	

Abbreviation: CI = Confidence Interval; GTM = Geometric Mean; LSM = Least Square Mean; LSMD = Least Square Mean Difference; SE = Standard Error

Note 1: Missing data will be replaced for the efficacy endpoint in the ITT analyses using the Last observation carried forward (LOCF) method.

Note 2: LSM, LSMD, 95% CI for LSMD, and p-values are based on an Analysis of Covariance (ANCOVA) model with baseline viral load on log10 scale as a covariate and treatment group as an independent variable.

Source: Listing 16.2.6.4

O:\Studies\EmitBio\EB-P12-01\Biometrics\Programs\Tables\xxx.sas ran on Month Day, Year at hh:mm on data from Month Day, Year.

Repeat Table 14.2.1.1 for the following:

Table 14.2.1.2 – Time-Weighted Average Change in Log10-Transformed Viral Load by RT-qPCR from Baseline to Day 8 for Per-Protocol Population
 (with Note 1 removed)

Table 14.2.2.1 – Log10-Transformed Viral Load via RT-qPCR by Visit for Intent-to-Treat Population

Study Visit	Statistics	4 Days RD-X19 (N=XX)	7 Days RD-X19 (N=XX)	Sham (N=XX)
Visit 1 /Day 1	N	XX	XX	XX
	Mean ± SD	XX.X ± XX.X	XX.X ± XX.X	XX.X ± XX.X
	Median	XX.X	XX.X	XX.X
	Min, Max	XX, XX	XX, XX	XX, XX
	Geometric Mean on Original Scale	XX.X	XX.X	XX.X
Visit 3 /Day 3	N	XX	XX	XX
	Mean ± SD	XX.X ± XX.X	XX.X ± XX.X	XX.X ± XX.X
	Median	XX.X	XX.X	XX.X
	Min, Max	XX, XX	XX, XX	XX, XX
	Geometric Mean on Original Scale	XX.X	XX.X	XX.X
Visit 4 /Day 5				
Visit 5 /Day 8				

Missing data will be replaced for the efficacy endpoint in the ITT analyses using the Last observation carried forward (LOCF) method.

Note: Geometric Means are computed by exponentiating (base 10) the Means of the log10-transformed viral load.

Source: Listing 16.2.6.4

O:\Studies\EmitBio\EB-P12-01\Biometrics\Programs\Tables\xxx.sas ran on Month Day, Year at hh:mm on data from Month Day, Year.

Repeat Table 14.2.2.1 for the following:

Table 14.2.2.2 – Log10-Transformed Viral Load via RT-qPCR by Visit for Per-Protocol Population
 (with footnote 1 removed)

Table 14.2.2.3 – Proportion of Subjects with At Least 95% Reduction by Visit in SARS-CoV-2 Viral Load via RT-qPCR

Population	Study Visit	Statistics	4 Days RD-X19	7 Days RD-X19	Sham
Intent-to-Treat	Visit 3 /Day 3	N	XX	XX	XX
		n (%) Subjects with >=95% Reduction	XX (XX.X)	XX (XX.X)	XX (XX.X)
	Visit 4 /Day 5	N	XX	XX	XX
		n (%) Subjects with >=95% Reduction	XX (XX.X)	XX (XX.X)	XX (XX.X)
	Visit 5 /Day 8	N	XX	XX	XX
		n (%) Subjects with >=95% Reduction	XX (XX.X)	XX (XX.X)	XX (XX.X)
Per-Protocol	Visit 3 /Day 3	N	XX	XX	XX
		n (%) Subjects with >=95% Reduction	XX (XX.X)	XX (XX.X)	XX (XX.X)
	Visit 4 /Day 5	N	XX	XX	XX
		n (%) Subjects with >=95% Reduction	XX (XX.X)	XX (XX.X)	XX (XX.X)
	Visit 5 /Day 8	N	XX	XX	XX
		n (%) Subjects with >=95% Reduction	XX (XX.X)	XX (XX.X)	XX (XX.X)

Note: Missing data will be replaced for the efficacy endpoint in the ITT analyses using the Last observation carried forward (LOCF) method.

Source: Listing 16.2.6.3

O:\Studies\EmitBio\EB-P12-01\Biometrics\Programs\Tables\xxx.sas ran on Month Day, Year at hh:mm on data from Month Day, Year.

Table 14.2.3 – Clearance of Viral Infection in Saliva via RT-qPCR

Population	Endpoint	Statistics	4 Days RD-X19	7 Days RD-X19	Sham
Intent-to-Treat	Time to Clearance of Viral Infection	N	XX	XX	XX
		n (%) Censored	XX (XX.X)	XX (XX.X)	XX (XX.X)
		Median of Time	XX.X	XX.X	XX.X
		25 th , 75 th Percentiles	XX.X, XX.X	XX.X, XX.X	XX.X, XX.X
		95% CI of Median	(XX.X, XX.X)	(XX.X, XX.X)	(XX.X, XX.X)
		P-value RX-X19 vs. Sham	0.XXX	0.XXX	
	Subjects Demonstrating Clearance of Viral Infection at Day 8/ET Visit	n (%)	XX (XX.X)	XX (XX.X)	XX (XX.X)
Per-Protocol	Time to Clearance of Viral Infection	N	XX	XX	XX
		n (%) Censored	XX (XX.X)	XX (XX.X)	XX (XX.X)
		Median of Time	XX.X	XX.X	XX.X
		25 th , 75 th Percentiles	XX.X, XX.X	XX.X, XX.X	XX.X, XX.X
		95% CI of Median	(XX.X, XX.X)	(XX.X, XX.X)	(XX.X, XX.X)
		P-value RX-X19 vs. Sham	0.XXX	0.XXX	
	Subjects Demonstrating Clearance of Viral Infection at Day 8/ET Visit	(%)	XX (XX.X)	XX (XX.X)	XX (XX.X)

Abbreviation: CI = Confidence Interval

Subjects with clearance of viral infection at baseline are excluded from the analysis of time-to-clearance of viral infection.

Note 1: Clearance of viral infection in saliva is defined as a negative test (Ct value ≥ 32) via RT-qPCR, i.e. achievement of [1] RP Ct =0, AND [2] Average N1 Ct =32 or Average N1 Ct ='Undetermined'. Subjects who did not achieve clearance at the last assessment of the study are considered censored at the time of the last assessment.

Note 2: Subjects who did not achieve clearance at the exit of study are considered censored.

Note 3: Percentiles and 95% CI of median are derived using the Kaplan-Meier method. P-values for treatment comparison are from Log Rank Test.

Source: Listing 16.2.6.4, 16.2.5.3

O:\Studies\EmitBio\EB-P12-01\Biometrics\Programs\Tables\xxx.sas ran on Month Day, Year at hh:mm on data from Month Day, Year.

Figure 15.1.1 - Kaplan-Meier Plot of Time to Clearance of Viral Infection for Intent-to-Treat Population

Figure 15.1.2 - Kaplan-Meier Plot of Time to Clearance of Viral Infection for Per-Protocol Population

Table 14.2.4 – COVID-19 Composite Severity Score by Visit

Population	Study Visit	Category	Statistics	4 Days RD-X19	7 Days RD-X19	Sham
Intent-to-Treat	Visit 1 /Day 1 (Baseline)	Actual Value	N	XX	XX	XX
			Mean \pm SD	XX.X \pm XX.X	XX.X \pm XX.X	XX.X \pm XX.X
			Median	XX.X	XX.X	XX.X
		Actual Value	Min, Max	XX, XX	XX, XX	XX, XX
			N	XX	XX	XX
	Visit 5 /Day 8	Actual Value	Mean \pm SD	XX.X \pm XX.X	XX.X \pm XX.X	XX.X \pm XX.X
			Median	XX.X	XX.X	XX.X
			Min, Max	XX, XX	XX, XX	XX, XX
		Change from Baseline	Mean \pm SD	XX.X \pm XX.X	XX.X \pm XX.X	XX.X \pm XX.X
			Median	XX.X	XX.X	XX.X
Per-Protocol	Visit 1 /Day 1 (Baseline)	Actual Value	Min, Max	XX, XX	XX, XX	XX, XX
			N	XX	XX	XX
			Mean \pm SD	XX.X \pm XX.X	XX.X \pm XX.X	XX.X \pm XX.X
		Actual Value	Median	XX.X	XX.X	XX.X
			Min, Max	XX, XX	XX, XX	XX, XX
	Visit 5 /Day 8	Actual Value	N	XX	XX	XX
			Mean \pm SD	XX.X \pm XX.X	XX.X \pm XX.X	XX.X \pm XX.X
			Median	XX.X	XX.X	XX.X
		Change from Baseline	Min, Max	XX, XX	XX, XX	XX, XX
			Mean \pm SD	XX.X \pm XX.X	XX.X \pm XX.X	XX.X \pm XX.X
			Median	XX.X	XX.X	XX.X
			Min, Max	XX, XX	XX, XX	XX, XX

Note: Missing data will be replaced for the efficacy endpoint in the ITT analyses using the Last observation carried forward (LOCF) method.

Source: Listing 16.2.6.1

O:\Studies\EmitBio\EB-P12-01\Biometrics\Programs\Tables\xxx.sas ran on Month Day, Year at hh:mm on data from Month Day, Year.

Table 14.2.5.1 – Time to Alleviation of COVID-19 Symptoms

Population	Statistics	4 Days RD-X19	7 Days RD-X19	Sham
Intent-to-Treat	N	XX	XX	XX
	n (%) Censored	XX (XX.X)	XX (XX.X)	XX (XX.X)
	Median of Time	XX.X	XX.X	XX.X
	25 th , 75 th Percentiles	XX.X, XX.X	XX.X, XX.X	XX.X, XX.X
	95% CI of Median	(XX.X, XX.X)	(XX.X, XX.X)	(XX.X, XX.X)
	P-value RX-X19 vs. Sham	0.XXX	0.XXX	
Per-Protocol	N	XX	XX	XX
	n (%) Censored	XX (XX.X)	XX (XX.X)	XX (XX.X)
	Median of Time	XX.X	XX.X	XX.X
	25 th , 75 th Percentiles	XX.X, XX.X	XX.X, XX.X	XX.X, XX.X
	95% CI of Median	(XX.X, XX.X)	(XX.X, XX.X)	(XX.X, XX.X)
	P-value RX-X19 vs. Sham	0.XXX	0.XXX	

Abbreviation: CI = Confidence Interval

Note 1: Alleviation of COVID-19 symptoms is defined as all eight symptoms assessed by the subject as none (0) or mild (1).

Note 2: Time to alleviation is calculated as the number of hours from the first dose to the time of the first occurrence of symptoms alleviation. Subjects who did not achieve alleviation at the last assessment of study are considered censored at the time of the last assessment.

Note 3: Percentiles and 95% CI of median are derived using the Kaplan-Meier method. P-values for treatment comparison are from Log Rank Test.

Source: Listing 16.2.6.1.2, 16.2.5.3

O:\Studies\EmitBio\EB-P12-01\Biometrics\Programs\Tables\xxx.sas ran on Month Day, Year at hh:mm on data from Month Day, Year.

Figure 15.2.1 - Kaplan-Meier Plot of Time to Alleviation of COVID-19 Symptoms for Intent-to-Treat Population

Figure 15.2.2 - Kaplan-Meier Plot of Time to Alleviation of COVID-19 Symptoms for Per-Protocol Population

Table 14.2.5.2 – Time to Sustained Alleviation of COVID-19 Symptoms

Population	Statistics	4 Days RD-X19	7 Days RD-X19	Sham
Intent-to-Treat	N	XX	XX	XX
	n (%) Censored	XX (XX.X)	XX (XX.X)	XX (XX.X)
	Median of Time	XX.X	XX.X	XX.X
	25 th , 75 th Percentiles	XX.X, XX.X	XX.X, XX.X	XX.X, XX.X
	95% CI of Median	(XX.X, XX.X)	(XX.X, XX.X)	(XX.X, XX.X)
	P-value RX-X19 vs. Sham	0.XXX	0.XXX	
Per-Protocol	N	XX	XX	XX
	n (%) Censored	XX (XX.X)	XX (XX.X)	XX (XX.X)
	Median of Time	XX.X	XX.X	XX.X
	25 th , 75 th Percentiles	XX.X, XX.X	XX.X, XX.X	XX.X, XX.X
	95% CI of Median	(XX.X, XX.X)	(XX.X, XX.X)	(XX.X, XX.X)
	P-value RX-X19 vs. Sham	0.XXX	0.XXX	

Abbreviation: CI = Confidence Interval

Note 1: Sustained alleviation of COVID-19 symptoms is defined as all eight symptoms assessed by the subject as none (0) or mild (1) AND no single symptom reoccurs later at a level above mild (1).

Note 2: Time to sustained alleviation is calculated as the number of hours from the first dose to the time of the occurrence of sustained symptoms alleviation. Subjects who did not

achieve sustained alleviation at the last assessment of the study are considered censored at the time of the last assessment.

Note 3: Percentiles and 95% CI of median are derived using the Kaplan-Meier method. P-values for treatment comparison are from Log Rank Test.

Source: Listing 16.2.6.1.2, 16.2.5.3

O:\Studies\EmitBio\EB-P12-01\Biometrics\Programs\Tables\xxx.sas ran on Month Day, Year at hh:mm on data from Month Day, Year.

Figure 15.3.1 - Kaplan-Meier Plot of Time to Sustained Alleviation of COVID-19 Symptoms for Intent-to-Treat Population

Figure 15.3.2 - Kaplan-Meier Plot of Time to Sustained Alleviation of COVID-19 Symptoms for Per-Protocol Population

Table 14.3.1.1 - Treatment-Emergent Adverse Events by System Organ Class and Preferred Term for Safety Population

System Organ Class Preferred Term	4 Days RD-X19 (N=XX) n (%)	7 Days RD-X19 (N=XX) n (%)	Sham (N=XX) n (%)
Subjects Reporting at Least One Adverse Event	XX (XX.X)	XX (XX.X)	XX (XX.X)
System Organ Class #1	XX (XX.X)	XX (XX.X)	XX (XX.X)
Preferred Term #1	XX (XX.X)	XX (XX.X)	XX (XX.X)
Preferred Term #2	XX (XX.X)	XX (XX.X)	XX (XX.X)
...			
System Organ Class #2	XX (XX.X)	XX (XX.X)	XX (XX.X)
Preferred Term #1	XX (XX.X)	XX (XX.X)	XX (XX.X)
Preferred Term #2	XX (XX.X)	XX (XX.X)	XX (XX.X)
...			

Counts reflect numbers of subjects reporting one or more TEAE that map to the MedDRA system organ class/preferred term. At each level of summarization (system organ class or preferred term), subjects reporting more than one TEAE are counted only once.

Source: Listing 16.2.7

O:\Studies\EmitBio\EB-P12-01\Biometrics\Programs\Tables\xxx.sas ran on Month Day, Year at hh:mm on data from Month Day, Year.

Table 14.3.1.2 - Treatment-Emergent Adverse Events by System Organ Class, Preferred Term and Severity for Safety Population

System Organ Class Preferred Term	Severity	4 Days RD-X19 (N=XX) n (%)	7 Days RD-X19 (N=XX) n (%)	Sham (N=XX) n (%)
Subjects Reporting at Least One Adverse Event	Mild	XX (XX.X)	XX (XX.X)	XX (XX.X)
	Moderate	XX (XX.X)	XX (XX.X)	XX (XX.X)
	Severe	XX (XX.X)	XX (XX.X)	XX (XX.X)
System Organ Class #1	Mild	XX (XX.X)	XX (XX.X)	XX (XX.X)
	Moderate	XX (XX.X)	XX (XX.X)	XX (XX.X)
	Severe	XX (XX.X)	XX (XX.X)	XX (XX.X)
Preferred Term #1	Mild	XX (XX.X)	XX (XX.X)	XX (XX.X)
	Moderate	XX (XX.X)	XX (XX.X)	XX (XX.X)
...	Severe	XX (XX.X)	XX (XX.X)	XX (XX.X)
...				
...				

Counts reflect numbers of subjects reporting one or more TEAE that map to the MedDRA system organ class/preferred term. At each level of summarization (system organ class or preferred term), subjects reporting more than one TEAE are counted only once (under the greatest reported severity).

Source: Listing 16.2.7

O:\Studies\EmitBio\EB-P12-01\Biometrics\Programs\Tables\xxx.sas ran on Month Day, Year at hh:mm on data from Month Day, Year.

Table 14.3.1.3 - Treatment-Emergent Adverse Events by System Organ Class, Preferred Term and Causality to Study Device for Safety Population

System Organ Class Preferred Term	Causality	4 Days RD-X19 (N=XX) n (%)	7 Days RD-X19 (N=XX) n (%)	Sham (N=XX) n (%)
Subjects Reporting at Least One Adverse Event	Not Related	XX (XX.X)	XX (XX.X)	XX (XX.X)
	Related	XX (XX.X)	XX (XX.X)	XX (XX.X)
System Organ Class #1	Not Related	XX (XX.X)	XX (XX.X)	XX (XX.X)
	Related	XX (XX.X)	XX (XX.X)	XX (XX.X)
Preferred Term #1	Not Related	XX (XX.X)	XX (XX.X)	XX (XX.X)
	Related	XX (XX.X)	XX (XX.X)	XX (XX.X)
...				
...				
...				

Counts reflect numbers of subjects reporting one or more TEAE that map to the MedDRA system organ class/preferred term. At each level of summarization (system organ class or preferred term), subjects reporting more than one TEAE are counted only once (under the greatest reported causality).

Source: Listing 16.2.7

O:\Studies\EmitBio\EB-P12-01\Biometrics\Programs\Tables\xxx.sas ran on Month Day, Year at hh:mm on data from Month Day, Year.

Table 14.3.1.4 –Treatment-Emergent Adverse Events by System Organ Class, Preferred Term and Study Day of Most Severe Observation for Safety Population

System Organ Class Preferred Term	Study Day*	4 Days RD-X19 (N=XX) n (%)	7 Days RD-X19 (N=XX) n (%)	Sham (N=XX) n (%)
Subjects Reporting at Least One Adverse Event	Day 1	XX (XX.X)	XX (XX.X)	XX (XX.X)
	Day 2	XX (XX.X)	XX (XX.X)	XX (XX.X)
	...			
System Organ Class #1	Day 1	XX (XX.X)	XX (XX.X)	XX (XX.X)
	Day 2	XX (XX.X)	XX (XX.X)	XX (XX.X)
	...			
Preferred Term #1	Day 1	XX (XX.X)	XX (XX.X)	XX (XX.X)
	Day 2	XX (XX.X)	XX (XX.X)	XX (XX.X)
	...			
...				
...				

*Study Day is calculated relative to date of first treatment. Day 1 is the day of first treatment. For the summary, Study Day is the day number when the most severe observation was made of an event.

